3.2. Participant Grouping

For analyses based on the All Randomized Analysis Set and FAS, participants will be grouped according to the treatment to which they were randomized. For analyses based on Safety Analysis Set, CCI Virology Analysis Set and CCI participants will be grouped according to the actual treatment they received.

The actual treatment received will differ from the randomized treatment only when their actual treatment differs from randomized treatment for the entire treatment duration.

3.3. Strata and Covariates

Participants will be randomly assigned to treatment groups via the interactive voice or web response system (IXRS) in a 2:1 ratio using a stratified randomization schedule. Randomization will be stratified by:

- ESKD requiring chronic dialysis (Yes, No)
- High-flow oxygen requirement (Yes, No)
- Region (US, ex-US)

Stratification discrepancies between the IXRS and the clinical database will be reviewed and assessed. The values recorded in the clinical database will be used for analyses in case there are discrepancies. Based on the assessment of stratification discrepancies, a sensitivity analysis of the primary endpoint may be performed.

The primary efficacy endpoint and the key α -controlled secondary efficacy endpoint (see Section 6 for definition) will be evaluated in a stratified analysis based on the same 3 factors used for randomization, as specified in Section 6. In addition, observed imbalances between treatment groups in other baseline characteristics may be considered as covariates in sensitivity analyses of efficacy endpoints.

3.4. Examination of Participant Subgroups

The primary efficacy endpoint and the key α -controlled secondary efficacy endpoint will be examined for the following participant subgroups:

- Kidney disease status (defined as: AKI, CKD and ESKD.)
- High-flow oxygen requirement at baseline (Yes, No)
- Region (US, ex-US)
- Participant's age (≥ 18 - < 65 , ≥ 65 years)
- Sex at birth: (a) male and (b) female
- Race: (a) Asian, (b) Black, (c) White, (d) Other
- Baseline risk factor (as applicable): Chronic lung disease (Yes, No), Hypertension (Yes, No), Cardiovascular or cerebrovascular disease (Yes, No), Diabetes mellitus (Yes, No), BMI (with categories: < 20 , ≥ 20 - < 30 , ≥ 30 kg/m²), Immunocompromised state (Yes, No), Chronic liver disease (Yes, No), Current cancer (Yes, No)

In addition, the primary efficacy endpoint will be examined for duration of symptoms prior to first dose of study drug (≤ 5 days vs > 5 days) and baseline oxygen support status. Other subgroups may be considered based on imbalances between treatment groups observed in other baseline characteristics.

3.5. Multiple Comparisons

To control the overall Type I error in the evaluation of the primary efficacy endpoint and the key secondary efficacy endpoint, the hypothesis testing will be performed in sequential order.

The primary efficacy endpoint will be tested first at the significance level of 0.05. If the primary efficacy endpoint null hypothesis is rejected, the key secondary efficacy endpoint will be tested at the 0.05 significance level; otherwise, the key secondary efficacy endpoint will not be tested.

All other endpoints may be tested using 2-sided tests at the 0.05 significance level without multiplicity adjustment as they are considered secondary **CCI** endpoints.

3.6. Missing Data and Outliers

3.6.1. Missing Data

In general, missing data will not be imputed unless methods for handling missing data are specified. Exceptions are presented in this document.

In this study, a missing pre-treatment laboratory result would be treated as normal (ie, no toxicity grade) for the laboratory abnormality summary.

For missing last dose date of study drug, imputation rules are described in Section 3.8.1. The handling of missing or incomplete dates for AE onset is described in Section 7.1.5.2, and for concomitant medications in Section 7.4.

Imputation rules for the secondary efficacy endpoints related to the 8-point ordinal scale score are described in Section 6.2.

3.6.2. Outliers

Outliers will be identified during the data management and data analysis process. No sensitivity analyses to evaluate the impact of outliers on efficacy or safety outcomes are planned. Unless specified otherwise, all data will be included in the analyses.

3.7. Data Handling Conventions and Transformations

In general, age collected at Day 1 (in years) will be used for analyses and presented in listings. If age at Day 1 is not available for a participant, then age derived from date of birth and the Day 1 visit date will be used instead. If an enrolled participant was not dosed with any study drug, the randomization date will be used instead of the Day 1 visit date. For screen failures, the date the first informed consent was signed will be used for the age derivation. Age required for longitudinal and temporal calculations and analyses (e.g., estimates of creatinine clearance, age at date of AE) will be based on age derived from date of birth and the date of the measurement or event, unless otherwise specified.

The following conventions will be used for the imputation of date of birth when it is partially missing or not collected:

- If only year of birth is collected, then “01 July” will be imputed as the day and month of birth
- If year of birth is missing, then date of birth will not be imputed.

Laboratory data that are continuous in nature but are less than the lower LOQ or above the upper LOQ will be imputed as follows:

- A value that is 1 unit less than the LOQ will be used to calculate descriptive statistics if the datum is reported in the form of “< x” (where x is considered the LOQ). For example, if the values are reported as < 50 and < 5.0, values of 49 and 4.9, respectively, will be used to calculate summary statistics. An exception to this rule is any value reported as < 1 or < 0.1, etc. For values reported as < 1 or < 0.1, a value of 0.9 or 0.09, respectively, will be used to calculate summary statistics.
- A value that is 1 unit above the LOQ will be used to calculate descriptive statistics if the datum is reported in the form of “> x” (where x is considered the LOQ). Values with decimal points will follow the same logic as above.
- The LOQ will be used to calculate descriptive statistics if the datum is reported in the form of “≤ x” or “≥ x” (where x is considered the LOQ).

CCI [REDACTED]

[REDACTED]

[REDACTED]

[REDACTED]

[REDACTED]

[REDACTED]

[REDACTED]

Natural logarithm transformation will be used for analyzing concentrations. Concentration values that are BLQ will be presented as “BLQ” in the concentration data listing. Values that are BLQ will be treated as 0 at predose time points, and one-half the value of the LOQ at postdose time points for summary purposes.

The following conventions will be used for the presentation of summary and order statistics:

- If at least 1 participant has a concentration value of BLQ for the time point, the minimum value will be displayed as “BLQ.”
- If more than 25% of the participants have a concentration data value of BLQ for a given time point, the minimum and Q1 values will be displayed as “BLQ.”

- If more than 50% of the participants have a concentration data value of BLQ for a given time point, the minimum, Q1, and median values will be displayed as “BLQ.”
- If more than 75% of the participants have a concentration data value of BLQ for a given time point, the minimum, Q1, median, and Q3 values will be displayed as “BLQ.”
- If all participants have concentration data values of BLQ for a given time point, all order statistics (minimum, Q1, median, Q3, and maximum) will be displayed as “BLQ.”

3.8. Analysis Visit Windows

3.8.1. Definition of Study Day

Study day will be calculated from the first dosing date of study drug and derived as follows:

- For assessment dates on or after the first dosing date: Assessment Date – First Dosing Date + 1
- For assessment dates prior to the first dosing date: Assessment Date – First Dosing Date

Therefore, Study Day 1 is the day of first dose of study drug administration.

Last Dose Date is defined as the maximum, nonmissing, nonzero dose end date of treatment recorded on the Study Drug Administration eCRF form with “Study Drug Permanently Withdrawn” box checked for participants who prematurely discontinued or completed study drug according to the Study Drug Completion eCRF.

Last dose date is not expected to be missing. However, if last dose date is missing, it will be imputed using the maximum of non-missing, non-zero dose, study drug start and stop dates.

Last Study Date is the latest of study drug start dates and end dates, the in-person or phone visit dates, the vital sign and the laboratory collection dates, including the Day 60 phone follow-up visit date. For participants who died during the study, the death date will be the Last Study Date. For participants who died after completing the study or after prematurely discontinuing the study, the death date will not be considered for the Last Study Date.

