7.3.3. Serious Adverse Events

All SAEs, regardless of cause or relationship, that occur after the participant first consents to participate in the study (ie, signing the ICF) and throughout the duration of the study, including the posttreatment follow-up visit, must be reported on the applicable eCRFs and Gilead GLPS (formerly known as Pharmacovigilance and Epidemiology) as instructed below in this section. This also includes any SAEs resulting from protocol-associated procedures performed after the ICF is signed.

Any SAEs and deaths that occur after the posttreatment follow-up visit but within 30 days of the last dose of investigational drug, regardless of causality, should also be reported.

Investigators are not obligated to actively seek SAEs after the protocol-defined follow-up period; however, if the investigator learns of any SAEs that occur after the protocol-defined follow-up period has concluded and the event is deemed relevant to the use of investigational drug, the investigator should promptly document and report the event to Gilead GLPS.

Instructions for reporting SAEs are described in Section [7.4.1](#).

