1.3. Sample Size and Power

A total of approximately 1116 participants are planned to be randomized in a 2:1 ratio to 2 groups (744 in the RDV group and 372 in the saline as placebo group).

This sample size achieves approximately 85% power to detect a hazard ratio of 0.70 at a two-sided alpha level of 0.05. In the sample size calculation, it is assumed that the event rate in the saline as placebo group is 35%. The hazard ratio and event rate in the saline as placebo group are based on the most conservative estimates of the primary endpoint (composite of all-cause mortality or IMV) and the key α -controlled secondary endpoint (all-cause mortality) through Day 29 among a subset of participants with eGFR < 60 mL/min in the Division of Microbiology and Infectious Diseases Protocol 20-0006 Adaptive COVID-19 Treatment Trial (ACTT)-1 (hazard ratio of 0.67 and placebo rate of 33%).

The sample size calculation was done using software EAST (Version 6.5, module for log-rank test given accrual duration [120 days] and study duration [149 days] and 1 interim analysis at 50% information fraction using the Lan-Demets approach with O'Brien-Fleming type spending function).

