6.1.3. Primary Analysis of the Primary Efficacy Endpoint

The primary endpoint will be analyzed using a stratified log-rank test stratified by the randomization strata. P value and the proportion of all-cause mortality or IMV at Day 29 from Kaplan-Meier estimate will be provided.

The hazard ratio and 95% confidence interval (CI) will be estimated using a Cox model with stratification factors as covariates.

Participants with missing outcomes for the primary endpoint due to premature discontinuation of the study on or prior to Day 29 will be censored at the last study day.

Additionally, the difference in proportions of all-cause mortality or IMV at Day 29 between treatment groups and the 95% CI for the difference will be provided based on the stratum-adjusted Mantel-Haenszel (MH) proportion as described in {Koch 1989} in [Appendix 2](#).

The FAS will be the primary analysis set for efficacy endpoint evaluation.

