6.1.4. Secondary Analyses of the Primary Efficacy Endpoint

The primary endpoint will also be analyzed for each of the subgroups defined in Section 3.4.

Sensitivity analyses maybe conducted using the following alternative approaches for the primary endpoint.

- A CMH test including stratification factors as strata for the statistical comparison between treatment groups. If a participant prematurely discontinues from the study prior to Day 29 with no event before discontinuation or the IMV/death status is missing, the participant will be considered as with no IMV/death.

- In rare occasions, a participant may be unblinded to site for safety considerations (Gilead remains blinded). Data for such participants after site unblinding may be censored for a sensitivity evaluation.

The sensitivity analyses are for the purposes of evaluating the robustness of the estimates of the primary analysis.

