7.1.6. Summaries of Adverse Events and Deaths

TEAEs will be summarized based on the Safety Analysis Set.

A brief, high-level summary of the number and percentage of participants who experienced at least 1 TEAE in the categories described below will be provided by treatment group. Treatment-emergent deaths observed in the study will also be included in this summary.

Treatment-emergent death refers to deaths that occurred between the first dose date and the last dose date plus 30 days (inclusive).

The number and percentage of participants who experienced at least 1 TEAE will be provided and summarized by SOC, High level term (HLT), PT, and treatment group.

For other AEs described below, summaries will be provided by SOC, PT, and treatment group:

- TEAEs with Grade 3 or higher
- TE study drug-related AEs
- TE study drug-related AEs with Grade 3 or higher
- TE SAEs
- TE study drug-related SAEs
- AEs leading to premature discontinuation of study drug

Multiple events will be counted only once per participant in each summary. Adverse events will be summarized and listed first in alphabetic order of SOC (and HLT within each SOC if applicable), and then by PT in descending order of total frequency within each SOC. For summaries by severity grade, the most severe grade will be used for those AEs that occurred more than once in an individual participant during the study.

In addition to the above summary tables, all TEAEs, TEAEs with Grade 3 or higher, TE study drug-related AEs, TE study drug-related AEs with Grade 3 or higher, and TE SAEs will be summarized by PT only, in descending order of total frequency.

The above summary tables may also be provided for one or more of the following subgroups: kidney disease status (as defined in Section 3.4), high-flow oxygen requirement (Yes, No), and/or region (US, ex-US).

In addition, data listings will be provided for the following:

- All AEs
- All study drug-related AEs
- All AEs with severity of Grade 3 or higher
- All SAEs
- All study drug-related SAEs
- All Deaths
- AEs leading to premature discontinuation of study drug

Listing of renal and hepatic adverse events will be provided. Hypersensitivity including infusion-related reactions adverse events will also be summarized and listed (See [Appendix 2](#)).

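### The optional CMH sensitivity analysis scores some known deaths by Day 29 as event-free, and the primary analysis never states that deaths after leaving the study count

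*SAP*

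**What the plan says.** - **Endpoint (SAP 6.1.1).** Death from any cause, or IMV, from first dose through Day 29. Nothing restricts it to time on study.
- **Primary analysis (SAP 6.1.3).** Stratified log-rank test and Cox model. Participants whose outcome is missing because they left the study on or before Day 29 "will be censored at the last study day". A Mantel-Haenszel (MH) difference in Day 29 proportions is also planned (formula in Appendix 2, item 13), with no rule for people who left.
- **Last Study Date (SAP 3.8.1).** A death while on study sets this date. A death in someone who had already left early does not: "after prematurely discontinuing the study, the death date will not be considered for the Last Study Date".
- **CMH sensitivity analysis (SAP 6.1.4, optional).** "If a participant prematurely discontinues from the study prior to Day 29 with no event before discontinuation", or if the status is missing, the participant is scored as having had neither IMV nor death.
- **Secondary endpoints (SAP 6.2.1).** Mortality is handled like the primary endpoint. Missing time-to-event outcomes are censored at the last known status for that endpoint. On the ordinal scale, a death on or before Day 29 is scored 8 from that day on.
- **Protocol 8.5.1.** Missing primary outcomes are censored at the date of last contact.
- **Safety (SAP 7.1.6).** Treatment-emergent death is defined by date: first dose to 30 days after last dose. Protocol 7.3.3 also asks for reports of "Any SAEs and deaths that occur after the posttreatment follow-up visit but within 30 days of the last dose of investigational drug".

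**The concern.** Mortality is one component of the primary composite and the whole of the key secondary endpoint. Whether a known death counts should therefore not depend on whether the participant was still formally in the study. SAP 6.1.4 says that for one analysis it does depend on that. SAP 6.1.3 and 3.8.1 leave a programmer room to reach the same result elsewhere.

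Patients who leave early may differ in risk from those who stay, and leaving may differ by arm. Scoring their known deaths as non-events lowers the event proportions and can shift the treatment contrast. The CMH analysis exists to test the robustness of the primary result. It cannot do that well if it discards observed events, and a discrepancy between the two analyses would then be hard to interpret.

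**Working it through.** **1. The plan's own figure.** SAP 1.3 states: "This sample size achieves approximately 85% power to detect a hazard ratio of 0.70 at a two-sided alpha level of 0.05". The other inputs there are a 35% placebo event rate and 744 and 372 participants.

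- RDV event rate under proportional hazards: 1 − (1 − 0.35)^0.70 = 26.0%. The planned difference is 35.0 − 26.0 = 9.0 points.
- Events: 372 × 0.35 + 744 × 0.2603 = 323.9.
- Schoenfeld power: Φ(√(323.9 × 2/9) × |ln 0.70| − 1.96) = 85.7%, or 85.6% with the planned interim look. The stated figure reproduces.

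**2. One case under each rule.** Take a dosed participant without IMV who leaves on Day 10 and is known to have died on Day 15.

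| Place | What triggers the rule | Result |
|---|---|---|
| SAP 6.1.1, endpoint | Death or IMV, first dose through Day 29 | Event |
| SAP 6.2.1, ordinal scale | Death on or before Day 29 | Category 8 |
| SAP 6.2.1, mortality | Missing outcome, censored at last known status | Event on the natural reading, since the last known status is dead |
| SAP 6.1.3, log-rank and Cox | Missing outcome due to leaving | Event if a known death is not a missing outcome; otherwise censored at the last study day |
| SAP 6.1.3, MH difference | None stated | Undetermined |
| SAP 6.1.4, CMH | Left without a prior event, **or** status missing | No IMV/death |
| SAP 7.1.6, safety | Date of death | Counted by date |

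Only the CMH row contradicts the endpoint outright. Its two conditions are alternatives, so the first applies even when status is known.

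**3. Safety window.** Dosing lasts 1 to 5 days. A last dose on Day 1 gives a window to Day 31 (1 + 30), and on Day 5 to Day 35 (5 + 30). Every death by Day 29 in a dosed participant therefore meets the date definition. The Full Analysis Set and the Safety Analysis Set both require at least one dose, so they hold the same people.

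**4. Size.** The documents give no count of leavers and no later mortality. The inputs below are assumptions: 3% to 8% leave event-free, and 30% to 50% of those are known to die by Day 29.

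- *CMH scoring.* Events missed = leaving rate × later death risk: 0.03 × 0.30 = 0.9 points, up to 0.08 × 0.50 = 4.0 points. If 3% left in one arm and 8% in the other, both with 50% later mortality, the arms would be distorted by (0.08 − 0.03) × 0.50 = 2.5 points relative to each other.
- *Censoring, if the primary analysis were read that way.* This product does not apply. The error depends on how leavers' risk differs from stayers' risk. With early leaving and 35% risk in stayers, it is 0.08 × (0.50 − 0.35) = 1.2 points at the upper end. At the lower end it is 0.03 × (0.30 − 0.35) = −0.15 points, a slight overestimate. The unequal-leaving case gives 0.05 × 0.15 = 0.75 points.
- *Power of the log-rank test.* If 5% of events were lost equally in both arms, 323.9 × 0.95 = 307.7 events remain and power is 83.9%. Enrollment stopped below half of 1116, so below 558. At planned rates that is at most 186 × 0.35 + 372 × 0.2603 = 161.9 events and 57.1% power. Five fewer events would give 55.8%.

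**The case against.** A reader might infer that known deaths after withdrawal are removed from the primary and key secondary analyses. The documents do not support that:

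- SAP 3.8.1 defines a date variable. It keeps a later-learned death from extending follow-up and says nothing about event status.
- SAP 6.1.3 censors only missing outcomes, and a dated death by Day 29 is most naturally not missing.
- SAP 3.8.3 says that a time-to-event analysis uses all data regardless of visit window. Appendix 2, item 18 imputes partial death dates even when the last clinical date is in an earlier month, so death dates are held apart from last contact.
- For mortality, censoring at last known status points towards counting the death.
- The CMH rule has a different trigger from SAP 6.1.3 and does not carry over to it.

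A reader might also infer that efficacy and safety tables must report different death counts. That is not certain either, because SAP 7.1.6 refers to deaths observed in the study.

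Nor is it shown that many such deaths will be in the database. The sentence quoted from Protocol 7.3.3 concerns deaths after the follow-up visit, and investigators need not actively seek events after the follow-up period. Stopping study drug is not leaving the study: Protocol 3.5, 5.1.3 and 6.11 keep such participants in follow-up.

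All of this stands, and it limits the point. It does not rescue the literal CMH rule. It also does not supply the missing statement that known deaths count, or reconcile the three censoring dates.

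**Conclusion.** The CMH rule in SAP 6.1.4 is wrong as written: it scores a known death by Day 29 as no event when the participant had already left. The analysis is optional and a sensitivity analysis, which limits the consequence. For the log-rank, Cox and MH analyses the plan is ambiguous, with counting the death the more natural reading of the first two. For mortality the text already leans that way.

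The size cannot be derived from the documents. The 0.9 to 4.0 points and the 2.5-point distortion rest wholly on assumed leaving and death rates, assume that every later death becomes known, and describe the CMH analysis only. They should not be carried over to the primary test. The correction is worth making because it is cheap and because, with fewer than about 162 events expected at planned rates, a few misclassified deaths are a larger share of the information than the design foresaw.

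**What to change.** 1. In SAP 6.1.4, replace the condition about events before discontinuation with: no event known on or before Day 29. The separate rule for missing status can stay as that analysis's stated assumption.
2. In SAP 6.1.3 and 6.2.1, state that any death dated from first dose through Day 29, from any source including SAE reports, is an event on that date in the primary, key secondary, MH and CMH analyses, whatever the participant's study status.
3. Censor only participants whose outcome is unknown. Choose one censoring date in place of the last study day (SAP 6.1.3), last known status (SAP 6.2.1) and date of last contact (Protocol 8.5.1), and define it so that it cannot override a known death.
4. Add to Appendix 2, item 13 how participants with unknown Day 29 status enter the MH difference.

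The cost is SAP wording and a small change to the event derivation, before unblinding. No new data are needed.
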